### **PRP Dosing and Protocol**

Several phlebotomy and processing kits are FDA approved for safe and rapid preparation of PRP, and are commercially available. Dose, preparation and regimen of intra-articular injections of PRP have been variable in the literature. Doses vary between one to three injections, given consecutively within one or two week intervals [30].

For this protocol, we will use the FDA approved Harvest PRP Procedure Pack kit (BK000037) from Terumo-Harvest. The Harvest PRP system is designed to be used for the safe and rapid preparation of autologous platelet-rich plasma (PRP) from a small sample of blood at the patient's point of care. Each Harvest PRP kit consists of components necessary to collect whole blood from the patient into a syringe containing anticoagulant and to separate the centrifuged sample into fractions (including the one containing platelet-rich plasma).

Each PRP preparation requires a total of 30 mL of peripheral blood. Blood will be obtained via direct venipuncture by radiology nursing staff, [name] or one of the study team physicians using the provided tourniquet and butterfly needle. Blood will be collected into a 30mL syringe containing 3mL ACDA. 30 mL of acid-citrate-dextrose Formula (ACD-A) anticoagulated whole blood will be processed according to the manufacturer's directions. In brief, the anticoagulated whole blood will be transferred into the first chamber, which has a floating shelf of a proprietary density. Following an initial centrifugation of 4 minutes, the supernatant, containing plasma and the cellular elements less dense than the floating shelf, will be decanted into the second chamber of the disposable and centrifuged for 10 minutes. The

PRP volume of 3 or 4 mL will be prepared using the appropriate spacer to remove the desired volume of the supernatant platelet-poor plasma (PPP). The PRP is resuspended in the remaining volume of PPP.

This PRP preparation process takes place in the Interventional Radiology suite, Flourosopy suite or a Co-Investigator's clinic office.

All sites/clinics are amenable for sterile procedures.

Immediately prior to PRP injection into the study subject, calcium chloride is drawn up from the activator ampoule and will be added to the PRP. The activated PRP will then be injected in its entirety into the knee joint. All the preparation is performed under strict aseptic technique and follows the appropriate manufacturer instructions.

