### **6 month Research MRIs**

- If the patient received their initial diagnostic MRI by a Non-contrast MRI, the patient will receive a Non-contrast MRI at their 6 month research MRI visit.
- If the patient received their initial diagnostic MRI by a dGEMRIC MRI, the patient will receive a dGEMRIC MRI at their 6 month research MRI visit.
- If the patient received their initial diagnostic MRI by a MRI with and without contrast, the patient will receive a Non-contrast MRI at their 6 month research MRI visit.

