### **Proposed statistical analysis for Aim 1: Cartilage healing**

The T1GD value on dGEMRIC measures GAG content in cartilage. Higher T1GD values are associated with higher GAG content in the tissue, a positive measure of cartilage health. We assume that the value is approximately normal.

We plan to fit a general linear mixed model [39] for the outcome of T1GD. Predictors will include the visit at which the T1GD test was performed (initial MRI and 6 months), whether the site was weight bearing or not, and whether the side was affected or not, and the treatment group. Age will be included as a covariate. An unstructured covariance will be used to account for correlation between T1GD measurements on the same participant. Jackknifed-studentized residuals will be examined to assess normality, and transformations will be applied as appropriate.

We will test the null hypothesis of no time by treatment by weight bearing surface by affected side interaction. Given a non-significant interaction, we will test the main effects of time and treatment, comparing the difference between the weight-bearing and non-weight bearing surface for the affected and non-affected sides. Estimates, 95% confidence intervals, and p-values will be produced. All hypothesis tests will be performed using the Wald test with Kenward and Roger degrees of freedom[40] . Hypothesis tests will be performed at the Bonferroni corrected alpha of  $0.05/3 = 0.017$ .

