### **Proposed statistical analysis for Aim 2: Functional Recovery and Symptoms**

We will analyze scores for each subscale of the KOOS-child, and the overall score produced by the pedi-IKDC range from 0 to 100, with higher scores indicating improved knee function. Each measure is approximately normal.

We describe the analysis for Aim 2, Sub-aim 2.1. The analyses for the other sub-aims are exactly parallel.

We plan to fit a general linear mixed model [39] with the pain subscale of the KOOS-child as the outcome. Predictors will include the visit at which the survey was given (6 weeks, 12 weeks, 6 months, 9 months and 12 months) and treatment group. Age will be included as a covariate. An unstructured covariance will be used to account for correlation between measurements on a single participant. If the resulting model fails to converge, a spatial exponential covariance will be used. Jackknifed-studentized residuals will be examined to assess normality, and transformations will be applied as appropriate.

We will test the null hypothesis of no polynomial time trend by treatment interaction. If the time-by-treatment test is non-significant, we will step down to test the main effects of time and treatment. Estimates, 95% confidence intervals, and p-values will be produced.

All hypothesis tests will be performed using the Wald test with Kenward and Roger degrees of freedom [40] . Three hypothesis tests may be performed for each outcome, for a total of 12 tests. To control for multiple comparisons, all hypotheses will be tested at the Bonferroni corrected alpha level of  $0.05/12=0.004$ .

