### **Power Analysis**

We conducted a power analysis for Aim 1, the primary endpoint of the study. The maximum sample size for the proposed trial is fixed at 12 patients per arm (24 participants total). The sample size is limited due to costs associated with dGEMRIC.

We calculated power for the test of no difference in T1GD between the treatment groups. We assumed a standard deviation of 50 ms for T1GD values, and a correlation of 0.2 between the baseline MRI and the 12-month T1GD measurements. Estimates were based on T1GD values reported by Neuman et al[42]. We expect T1GD values to be 85 ms higher in the injection group when compared to conservative therapy at the 6 month time point with no difference at baseline. We calculated power for 10, 11, or 12 participants per arm. Power was calculated using GLIMMPSE version 2.0.1.[43]

To detect a mean difference of 85 ms in T1GD between the treatment groups, power will be 0.93 with a Type I error rate of 0.05, for 12 participants per treatment group. To ensure a conclusive study, we will target an effective sample size of 10 participants per group. Over the 12 months, we expect to lose up to two participants per treatment group. To account for the attrition, we have set an enrollment goal of 24 participants, or 12 participants per treatment group.

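### The Aim 1 test sequence contains no direct between-arm comparison of 6-month T1GD or of its change, so it can miss the 85 ms effect that the trial was powered for

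*Combined protocol and SAP*

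**What the plan says.** The Aim 1 section fits a mixed model to T1GD. The predictors are visit (initial MRI and 6 months), weight-bearing status, affected side and treatment, with age as a covariate. Baseline T1GD is therefore an outcome row, not a covariate. The testing order is:

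- First: "We will test the null hypothesis of no time by treatment by weight bearing surface by affected side interaction".
- Then: "Given a non-significant interaction, we will test the main effects of time and treatment", with the qualifier "comparing the difference between the weight-bearing and non-weight bearing surface for the affected and non-affected sides".
- Each test is at 0.05/3 = 0.017.

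Nothing is specified for the case where the four-way test is significant.

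The Power Analysis names Aim 1 as the primary endpoint and says "We calculated power for the test of no difference in T1GD between the treatment groups". The expected effect is 85 ms "at the 6 month time point with no difference at baseline". The section does not say at which of the four measured sites the 85 ms arises. Stated power is 0.93 at 0.05 with 12 per arm.

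For Aim 2 the plan does include the corresponding test: "We will test the null hypothesis of no polynomial time trend by treatment interaction".

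**The concern.** A difference that is absent at baseline and present at 6 months is a time-by-treatment effect. The Aim 1 list goes from the four-way term straight to main effects and never tests it.

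Neither listed treatment test replaces it. The four-way term asks whether the lesion site gains more than the other three sites of the same knee predict. The treatment main effect averages in a visit at which no patient has been treated. The time main effect pools the arms and says nothing about PRP.

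An effect shared across sites cannot be excluded, because "The activated PRP will then be injected in its entirety into the knee joint".

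The primary analysis could therefore report no significant effect although the planned benefit is present. Whether it does would depend on where in the knee the benefit lies and on how one ambiguous clause is read after the data are in.

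**Working it through.** **Inputs from the documents.** Effect 85 ms at 6 months and 0 at baseline; SD 50 ms; between-visit correlation 0.2; 12 per arm enrolled, 10 per arm after expected losses; alpha 0.05 (Power Analysis) or 0.05/3 = 0.0167 (Aim 1 analysis). The Power Analysis attaches the 0.2 to a 12-month T1GD measurement, although T1GD is measured at 6 months; it is used here as given.

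**Method.** Two-sided two-sample noncentral t on one contrast per patient, noncentrality = difference / (SD × √(2/n)), df = 2n − 2 (2n − 3 when baseline-adjusted). Age is omitted and data are taken as complete.

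**The plan's 0.93.** With 12 per arm at two-sided 0.05:

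- 6-month difference (SD 50): 0.978
- baseline-adjusted (SD 50√0.96 = 48.99): 0.982
- change (SD 50√1.6 = 63.2): 0.882

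None is within two points of 0.93. The nearest match found is the 6-month difference at 0.0167, which gives 0.932. So 0.93 is attainable, but for a test that the Aim 1 section does not list.

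**Treatment main effect, one site.** This is an illustration that needs only the plan's figures. Difference = (0 + 85)/2 = 42.5 ms; SD = 50√((1 + 0.2)/2) = 38.73.

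- 12 per arm: 0.73 at 0.05, 0.55 at 0.0167
- 10 per arm: 0.64 at 0.05, 0.45 at 0.0167

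**Four-way contrast.** In changes from baseline it is (affected WB − affected non-WB) − (unaffected WB − unaffected non-WB), where WB is weight-bearing.

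- Lesion only: 85 − 0 − 0 + 0 = 85
- Both affected-side sites: 85 − 85 = 0
- Both WB sites: 85 − 85 = 0
- All four sites: 0 − 0 = 0

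The zeros are algebra and need no assumed figure.

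**Full sequence, four sites.** The documents give no between-site correlation r. Assume r = 0.2, 0.5, 0.7 or 0.8, equal SDs, and a cross-visit, cross-site correlation of 0.2r.

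- Four-way SD = √(8 × 2500 × (1 − r) × 0.8) = 113.1, 89.4, 69.3, 56.6. Lesion-only power at 0.0167 with 10 per arm: 0.20, 0.33, 0.55, 0.76.
- Reading (a), treatment averaged over sites and visits: difference 85/8 = 10.6 (lesion only), 21.25 (two sites) or 42.5 (all sites); SD = 38.73√((1 + 3r)/4) = 24.5, 30.6, 34.1, 35.7.
- Reading (b), WB minus non-WB on the affected side, pooled over visits: difference 42.5 (lesion only or both WB sites) or 0 (both affected-side sites or all sites); SD = 38.73√(2(1 − r)) = 49.0, 38.7, 30.0, 24.5.

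Probability that the four-way or the treatment test is significant (10 per arm, 0.0167, 20,000 simulated trials per case), for r = 0.2 / 0.5 / 0.7 / 0.8:

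| Where the 85 ms lies | Reading (a) | Reading (b) |
|---|---|---|
| Lesion only | 0.25 / 0.36 / 0.57 / 0.76 | 0.42 / 0.63 / 0.87 / 0.97 |
| Both affected-side sites | 0.29 / 0.18 / 0.15 / 0.14 | about 0.03 |
| Both WB sites | same as row above, by symmetry | about 0.28 / 0.46 / 0.71 / 0.88 |
| All four sites | 0.88 / 0.68 / 0.57 / 0.53 | about 0.03 |

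Two tests at 0.0167 give about 0.03 by chance alone.

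**Direct contrast.** Lesion site at 6 months, baseline-adjusted: difference 85, SD 48.99. It depends neither on r nor on the other three sites.

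| Per arm with paired dGEMRIC | alpha 0.05 | alpha 0.0167 |
|---|---|---|
| 10 | 0.955 | 0.875 |
| 8 | 0.89 | 0.75 |
| 6 | 0.76 | 0.55 |

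The 8 and 6 are illustrative; the documents do not project how many patients will have paired dGEMRIC.

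**The case against.** The four-way term contains time and treatment. It is a between-arm test of lesion change relative to reference cartilage in the same knee, and that referencing looks deliberate: the imaging methods and the closing summary both use other cartilage sites for comparison. Exact zeros require the other sites to gain exactly as much as the lesion, and no section predicts an 85 ms gain in unaffected cartilage. With a graded effect (say 85 ms at the lesion and 30 ms at the other three sites) the four-way contrast is 85 − 30 − 30 + 30 = 55 ms. Sequence power with 10 per arm is then 0.29 to 0.43 on reading (a) and 0.18 to 0.65 on reading (b). The 0.73 and 0.55 describe one site, whereas the model has four. The multi-site figures rest on an assumed correlation.

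Much of this is fair. The plan does not always miss the effect: a lesion-only effect with highly correlated sites, or an all-site effect with weakly correlated ones, is found reasonably often. The one-site figures illustrate the dilution and are not the power of the planned model. But the graded case still has low power. A third reading of the qualifier, the surface difference compared between sides, is also zero for every shared pattern above. The promised estimates and confidence intervals could display the needed contrast but do not pre-specify it. None of these points supplies the missing test.

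**Conclusion.** The concern holds. The comparison that was powered does not appear among the Aim 1 tests, and the tests that do appear answer other questions. This follows from the text, as do the zero four-way contrasts and the halving of the treatment effect to 42.5 ms. The size of the loss depends on effect location, on the reading of the step-down and on between-site correlation, which the documents do not give. With 10 per arm at 0.0167 and r from 0.2 to 0.8, power ranges from chance (about 0.03) to 0.97. An effect on both affected-side sites is mostly missed on either reading (at most 0.29). The conclusion does not require the stated 0.93 to be miscalculated.

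**What to change.** 1. Name one primary Aim 1 contrast: PRP minus conservative in T1GD at the affected weight-bearing (lesion) site at 6 months. Either adjust for baseline T1GD or constrain the baseline means to be equal across arms in the mixed model.
2. Test it at 0.05 if it is the only primary Aim 1 test, otherwise at 0.0167.
3. Restate power for that contrast and alpha, using the number of patients expected to have paired dGEMRIC. Patients whose diagnostic scan was not dGEMRIC contribute no T1GD, since "the patient will receive a Non-contrast MRI at their 6 month research MRI visit".
4. Keep the four-way and lower-order site interactions as supportive within-knee comparisons. Write the step-down contrast out explicitly and say what follows a significant interaction.
5. Do not use the visit-pooled treatment main effect or the time main effect as tests of efficacy.

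The cost is revised analysis wording and a new power statement; no extra scans are needed. Constraining the baseline means stays within the planned mixed model, while covariate adjustment is a modest change of model. The real concession is that the within-knee reference comparison becomes supportive rather than primary.

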### **Proposed statistical analysis for Aim 2: Functional Recovery and Symptoms**

We will analyze scores for each subscale of the KOOS-child, and the overall score produced by the pedi-IKDC range from 0 to 100, with higher scores indicating improved knee function. Each measure is approximately normal.

We describe the analysis for Aim 2, Sub-aim 2.1. The analyses for the other sub-aims are exactly parallel.

We plan to fit a general linear mixed model [39] with the pain subscale of the KOOS-child as the outcome. Predictors will include the visit at which the survey was given (6 weeks, 12 weeks, 6 months, 9 months and 12 months) and treatment group. Age will be included as a covariate. An unstructured covariance will be used to account for correlation between measurements on a single participant. If the resulting model fails to converge, a spatial exponential covariance will be used. Jackknifed-studentized residuals will be examined to assess normality, and transformations will be applied as appropriate.

We will test the null hypothesis of no polynomial time trend by treatment interaction. If the time-by-treatment test is non-significant, we will step down to test the main effects of time and treatment. Estimates, 95% confidence intervals, and p-values will be produced.

All hypothesis tests will be performed using the Wald test with Kenward and Roger degrees of freedom [40] . Three hypothesis tests may be performed for each outcome, for a total of 12 tests. To control for multiple comparisons, all hypotheses will be tested at the Bonferroni corrected alpha level of  $0.05/12=0.004$ .

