**2. Specific Aims:**

In adolescents with osteochondritis dissecans of the knee:

**Aim 1.** Compared to conservative therapy alone, determine whether intra-articular platelet injections combined with conservative therapy lead to greater cartilage healing.

**Efficacy Endpoint** – Measurement by glycosaminoglycan (GAG) content (T1GD) on dGEMRIC, or by healing changes of MRI diagnostic cartilage sequences, using the DiPaola classification system.

**Aim 2.** Compared to conservative therapy, determine whether intra-articular platelet injections lead to improvements over time in:

**Efficacy Endpoint 2.1.** Pain, as measured by the pain subscale of the KOOS-child.

**Efficacy Endpoint 2.2.** Performance of activities of daily living, as measured by the ADL subscale of KOOS-child.

**Efficacy Endpoint 2.3.** Sport performance, as measured by the sports subscale of the KOOS-child.

**Efficacy Endpoint 2.4.** Overall function and symptom reduction, as measured by the pedi-IKDC.

**Aim 3.** Correlate dGEMRIC findings or MRI diagnostic cartilage sequence findings on imaging studies with measures of functional recovery and symptom reduction.

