### **Randomization**

After consent, the study personnel will open a sealed envelope containing the randomization assignment. The envelopes will also contain the appropriate patient handouts and instructions. Randomization will be balanced within the study to allow equal assignment to each treatment group. The randomization envelopes will be prepared by [name], the study biostatistician or her designated staff, using a random balanced allocation randomization protocol.

A study ID participant list in REDCap will be filled out by [name]/[name], their research staff or the Radiology Research Associate, [name], and will record the treatment assignment. The study personnel will e-mail the study statistician with the patient's study id number and the treatment assignment, recorded as 1 or 2. The study personnel will keep a key file containing the patients' names and study id numbers.

The study will not be blinded to the patient, to the patient's parent, or the physician administering the PRP injections. However, the study imaging and results will be kept blinded to the PI, [name], Pediatric Radiologist and the study biostatistician until the blind is broken, shortly before manuscript submission. Thus, treatment assignment will simply be recorded as 1 or 2 for the datasets.

The informed consent will make it clear to the patient and the patient's parents that the child will be randomized to one of two treatments: platelet-rich plasma injection with standard of care, or standard of care alone. Some patients may not like their assignment. If the patient wishes to, the patient who does not like their assignment can at that point drop out of the study and proceed with whatever care they choose. Such randomization related dropouts will be recorded.

This participant list in REDCap will contain the following information: At a minimum, empty columns are provided to record the following:

- Subject name
- Medical record number
- Patient and parent email addresses
- Initials of person enrolling the subject
- Date of enrollment.
- Treatment assignment
- List of required surveys to indicate completion

Other empty columns can be added on request.

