### **PRP and Conservative Treatment Schedules Following Randomization**

Patients will be assessed during a standard of care visit for basic eligibility to participate in this study or via a telephone call with one of the Study Team Physicians. Patients who meet the basic inclusion criteria will be given the option of participating in the study either at this first visit, or a subsequent visit after they are given the opportunity to review the informed consent documents.

**PRP study participants:** A total of 8 visits (9 visits, if consent is done as a separate visit) are expected during a 12-month time period for patient follow up. All initial visits will include a patient assessment using basic standard of care to determine eligibility for study enrollment. This first visit, if the patient decides to enroll, may also include patient consenting. The second through fourth visits, one week apart +/- 10 days, will include treatment with PRP injections. After the 3rd injection, subjects will be seen for clinical evaluation and survey assessment per schedule of assessment below as the standard of care. MRI obtained prior to enrollment for initial evaluation of the knee is performed as standard of care in the management of knee OCD. The research MRI performed at 6 months post treatment will be obtained to assess cartilage healing utilizing physiologic imaging of cartilage with the dGEMRIC technique or a Non-contrast MRI of the knee.

The three injection visits (1 through 3) will take approximately 30-45 minutes per visit. This includes time for the baseline patient reported outcomes and blood draw.

Follow up visits (5 through 9) last around 30 minutes and will include patient reported surveys, physical examination, and x-rays to assess the injury in accordance with the standard of care at CHCO.

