## **Informational patient brochure/Compliance Surveys/ Baseline and Follow-up KOOS and IKDC surveys/Clinical Assessments**

An informational brochure (see attached) will be used to assist in the recruitment of eligible patients. The brochure will describe the autologous platelet rich plasma treatment, process, risks, appointment information and post procedure information.

Patients randomized to the PRP Treatment arm will receive a Pre and Post-Injection Instruction handout (see attached). The handout describes how the patient should prepare for the PRP injections and what to expect after the injection.

The study personnel who consents the patient will request the patient's and parent's email addresses which will be used to send out the weekly and monthly surveys.

For the first 6 weeks of the study, all patients will receive a weekly Compliance Survey (see attached) created by the Sports Medicine physicians to validate compliance with 1. non-weight bearing, 2. wearing a brace, 3. at home PT exercises, and 4. no high impact activity.

**KOOS/IKDC surveys:** All patients will receive a baseline survey and repeat surveys at 6 wks, 12 wks, 6 m, 9m, and 12 months, which is considered standard of care, on the CHCO main campus or one of the following satellite locations (South, Parker, Centennial, Uptown/St Joseph's or Broomfield). The surveys will include the following outcome scales: Pedi IKDC and KOOS-child.

The Pedi-IKDC is a modified version of the widely used International Knee Documentation Committee (IKDC) Subjective Knee Form, which is a knee specific measure of symptoms, function and sports activity. The Pedi-IKDC was developed for use with children and adolescents ages 10-17. The reliability and validity of the Pedi-IKDC has been demonstrated to be acceptable in young patients with a variety of knee disorders.

Similarly, the KOOS – child is a pediatric version of the Knee Injury and Osteoarthritis Outcome Score (KOOS). The KOOS-child score is subdivided and scored in five categories: Pain, Other Disease-Specific Symptoms, Activities of Daily Living Function (ADL), Sport and Recreation Function and Knee-related Quality of Life (QOL).

[http://www.actaorthop.org/sup\\_files/5292.pdf](http://www.actaorthop.org/sup_files/5292.pdf)

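### The Aim 2 models leave out the baseline KOOS-child and pedi-IKDC scores that the protocol collects, which costs precision on the treatment main effect and leaves change up to week 6 unmodelled

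*Combined protocol and SAP*

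**What the plan says.** The section on KOOS/IKDC surveys states: "All patients will receive a baseline survey and repeat surveys at 6 wks, 12 wks, 6 m, 9m, and 12 months". The surveys are the KOOS-child and the pedi-IKDC.

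Aim 2 (Specific Aims) is to "determine whether intra-articular platelet injections lead to improvements over time in" pain, daily activities, sport, and overall function and symptoms, compared with conservative therapy.

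The Aim 2 analysis section lists the predictors as "the visit at which the survey was given (6 weeks, 12 weeks, 6 months, 9 months and 12 months) and treatment group", then adds: "Age will be included as a covariate". The covariance is unstructured, with a spatial exponential fallback. The first test is stated as "We will test the null hypothesis of no polynomial time trend by treatment interaction". If it is not significant, the main effects of time and treatment are tested. The other three outcomes are handled in the same way, and each test is held to 0.05/12.

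No other section brings the baseline scores into an analysis. The Aim 1 model, by contrast, includes the initial MRI as a level of visit.

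**The concern.** Two things follow from leaving baseline out.

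- **Precision.** Stable differences between patients that baseline would explain stay in the error of the treatment main effect. Aim 2 has no power calculation of its own, a strict per-test alpha, and only 10 to 12 patients per arm.
- **Fit to the aim.** The time terms begin at week 6. If a benefit is complete by week 6 and then held, the time-by-treatment interaction in this model is zero. The benefit can appear only in the step-down treatment main effect, which is the test that baseline adjustment would sharpen. Change from baseline to week 6, the period of injections and bracing, is not estimated.

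**Working it through.** **The plan's own figure.** Three tests on each of four outcomes make 12 tests. 0.05/12 = 0.00417, printed as 0.004, so it reproduces. No Aim 2 power is stated.

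**Inputs.** Five follow-up visits (Aim 2 analysis section). 12 per arm enrolled and 10 per arm after expected losses (Power Analysis). The only correlation in the documents is for another measure: "a correlation of 0.2 between the baseline MRI and the 12-month T1GD measurements". For KOOS-child and pedi-IKDC, rho is therefore an assumed range. The 1-SD effect, constant over visits, is also an assumption.

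**Variance of a patient's five-visit mean**, in units of the single-visit variance, with equal variances and a common rho among baseline and all visits:

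- without baseline: (1 + 4 rho)/5
- with baseline as covariate: (1 + 4 rho)/5 − rho²

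Estimating one more slope with age already in the model multiplies the adjusted variance by about (N − 4)/(N − 5). This is 20/19 = 1.053 for N = 24 and 16/15 = 1.067 for N = 20.

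**Power** is from the noncentral t, two-sided at 0.05/12, with noncentrality 1/√(2V/n). Degrees of freedom are N − 3 without baseline and N − 4 with it. Example for rho 0.5 and 12 per arm:

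- without: V = 0.60, standard error √(2 × 0.60/12) = 0.316, noncentrality 3.16, power 0.50
- with: V = 0.35 × 1.053 = 0.368, standard error 0.248, noncentrality 4.04, power 0.77

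| rho | V without | V with | ratio | ratio after cost, N = 24 | power, 12 per arm | power, 10 per arm |
|---|---|---|---|---|---|---|
| 0.2 | 0.36 | 0.32 | 0.89 | 0.94 | 0.79 to 0.82 | 0.66 to 0.68 |
| 0.3 | 0.44 | 0.35 | 0.80 | 0.84 | 0.68 to 0.77 | 0.54 to 0.63 |
| 0.5 | 0.60 | 0.35 | 0.58 | 0.61 | 0.50 to 0.77 | 0.37 to 0.63 |
| 0.7 | 0.76 | 0.27 | 0.36 | 0.37 | 0.37 to 0.89 | 0.27 to 0.78 |

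A simulation with 12 per arm (20,000 runs, age slope also estimated) gave 0.76 to 0.80, 0.65 to 0.75, 0.47 to 0.75 and 0.36 to 0.88. The levels are 1 to 3 points lower and the pattern is the same.

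**Where it stops paying.** At rho 0.1 the ratio after cost is (0.27/0.28) × 1.053 = 1.015 with 12 per arm and (0.27/0.28) × 1.067 = 1.029 with 10 per arm, a slight loss. Break-even is at rho of about 0.12 and 0.14.

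**Correlation that decays with time.** Take exponential decay over weeks 0, 6, 12, 26, 39 and 52, with 12 per arm:

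| correlation over 6 weeks | ratio | ratio after cost | power |
|---|---|---|---|
| 0.5 | 0.915 | 0.96 | 0.86 to 0.88 |
| 0.7 | 0.785 | 0.83 | 0.67 to 0.77 |
| 0.9 | 0.429 | 0.45 | 0.39 to 0.83 |

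**Which test gains.** A baseline covariate with one slope for all visits shifts every visit of a patient by the same amount. It cancels from within-patient time contrasts, so the time-by-treatment test is essentially unchanged. The gain is confined to the treatment main effect.

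**The case against.** The strongest reply concerns size. The large gains need baseline to stay well correlated with the scores a year later. The documents do not show this, and the plan's own spatial exponential fallback implies decay. Under decay, a six-week correlation of 0.5 gives almost nothing. That is correct, and the gain must be called unknown. Even so, it does not become a material loss: the worst case shown here is about 3% more variance.

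Second, the covariate does not help the first test, and the powers above are for the main effect taken alone, not for the two-step procedure. This also stands. But a sustained benefit reached by week 6 is seen only in that main effect.

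Third, improvement relative to conservative therapy can be read as the follow-up comparison, which is unbiased without baseline. That reading is fair. It answers any charge of bias but not the lost precision.

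Fourth, there are practical costs. The protocol says that patients will receive the survey, not that all will complete it, and a patient without a baseline score would drop out of a covariate model. Baselines taken after assignment was known cannot be repaired later. Both points stand and are taken into the fix.

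Aim 2 is also not the primary aim.

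**Conclusion.** The concern holds. Baseline KOOS-child and pedi-IKDC are scheduled for all patients and used in no analysis. The planned comparison remains valid, so this is lost efficiency and an incomplete match to the aim, not bias.

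Under equal correlation, and after the small-sample cost with 12 per arm, omitting baseline inflates the main-effect variance by about 1.07 at rho 0.2 (1/0.94), 1.6 at 0.5 (1/0.61) and 2.7 at 0.7 (1/0.37). Under fast decay the inflation is only a few per cent. These sizes rest on assumed correlations, and the powers also on an assumed constant 1-SD effect. The change should be made because the possible gain is large and the possible loss is slight.

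**What to change.** 1. In each of the four Aim 2 models, add the baseline value of the same score as a covariate alongside age. This is one line of text and one degree of freedom, and needs no new data. State how a missing baseline score is handled, for example by imputing the overall baseline mean, so that no patient is dropped.
2. State that the baseline survey is completed before assignment is revealed. The Randomization section says "After consent, the study personnel will open a sealed envelope containing the randomization assignment". The treatment schedule, describing the time allowed for the injection visits, says "This includes time for the baseline patient reported outcomes and blood draw". Patients and parents are not blinded, so a self-reported baseline given after assignment is known could be affected by it. This is one sentence, and possibly a change in the order of steps at the visit. Any baseline already taken after the envelope was opened should be flagged.
3. If the time-by-treatment test is meant to capture change from baseline, the covariate will not do it. A separate, non-equivalent option is to enter baseline as a sixth response visit with the arm means constrained equal there, and to define the treatment main effect over the five follow-up visits. Without these steps, an effect averaged over six visits would be diluted to 5/6. The cost is an unstructured covariance with 6 × 7/2 = 21 parameters instead of 5 × 6/2 = 15, estimated from 20 to 24 patients. The risk of non-convergence is higher, and the existing spatial exponential fallback would apply.
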